### 4.2. Interim Analysis and Data Monitoring

No interim analyses for review of efficacy are planned for this study.

Data and Safety Monitoring Board (DSMB) will be responsible for the periodic review of available study data. Refer to the DSMB Charter for additional details of deliveries and timings of DSMB meetings.

## 5. Analysis Populations

The following analysis populations are planned for this study. As per protocol, the 50mg QW group will not be included in analysis population. Main efficacy and safety data for those subjects will be listed.

- **Safety Population (SAF):** The SAF consists of all randomized subjects who receive at least one dose of study drug (active or placebo). SAF inclusion and reporting will be evaluated separately for each Stage so there will be a safety set defined for Stage 1 (randomized subjects who receive at least one dose of study drug (active or placebo) during Stage 1 and a safety set defined for Stage 2 (randomized subjects who receive at least one dose of study drug (active or placebo) during Stage 2). Subjects in the SAF will be analyzed according to the treatment they actually received. For definition of actual treatment see Section [6.1.4](#). Unless otherwise specified, all safety analyses will be conducted on the Safety Population.
- **Intent-To-Treat (ITT) Population:** The ITT Population will consist of all randomized subjects. Subjects in the ITT Population will be analyzed according to the treatment they are assigned at randomization. The primary efficacy analysis will be performed on the ITT Population. Unless otherwise specified, all other efficacy analyses also will be conducted on the ITT Population. Subject data for each Stage is included in ITT analyses based on the availability of randomization assignments. As efficacy results are also presented by Stage, an ITT Stage 1 population will be created (all randomized subjects) and an ITT Stage 2 population will be created (all randomized subjects entering Stage 2).
- **Modified Intent-To-Treat (mITT) Population:** The mITT Population will consist of all ITT subjects who received at least 2 weeks of study drug and had at least one post-dose measurement of CAPS-5 (CAPS-5 questionnaire must be complete.) Subjects in the mITT Population will be analyzed according to the treatment they are assigned at randomization. This analysis population will serve as sensitivity analysis for primary efficacy analysis. As efficacy results are also presented by Stage, a mITT Stage 1 population will be created (all mITT subjects) and a mITT Stage 2 population will be created (all mITT subjects entering Stage 2).
- **Per-Protocol Population (PP):** The PP Population will consist of all ITT Population subjects who do not incur a major protocol violation that would challenge the validity of their data (including compliance assessment). This population will be used to evaluate the sensitivity of the primary efficacy analysis. For the same reason as ITT population, a PP Stage 1 population (subjects from ITT without any major protocol deviation) and a PP Stage 2 population (subjects from ITT without any major protocol deviation entering Stage 2) will be created.

## 6. General Issues for Statistical Analysis

### 6.1. Statistical Definitions and Algorithms

#### 6.1.1. Baseline

The last non-missing observation recorded prior to the first dose of study drug (NYX-783 or placebo) will be used as the baseline observation for all calculations of change from baseline for Stage 1 data. For purposes of safety evaluation, subjects that are re-randomized in Week 4, the last non-missing observation before Week 4 will be used as baseline for Stage 2 data, with exception of groups [4] and [7] as referenced in [Figure 1](#). Changes from baseline for these groups will be based on the Stage 1 baseline given their study intervention remained unchanged.

For purposes of efficacy analyses, baseline values for Stage 2 data within all groups [4], [5], [6], [7], [8], [9], [10], and [11] will be based on the last assessment prior to first dose of study drug in Stage 2.

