#### **9.4. Week 2, Day 14 ( $\pm 7$ days)**

- S-STS (since last visit version)
- Vital sign measurements (after at least 5 minutes of rest, sitting or supine)
- Body weight
- Laboratory tests: clinical chemistry (fasted)
- Clinical outcome measures
  - CAPS-5
  - PCL-5
  - HADS
  - PSQI
  - PSQI-A
  - CGI-S
- Study drug accountability, compliance review, and dispensing
  - Medication adherence and reminder system review
- Concomitant medications
- AEs (serious and non-serious)

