#### **9.5. Stage 2: Week 4, Day 28 ( $\pm 3$ days)**

Study drug (including extra kit) dispensed in Stage 1 may not be re-dispensed and/or administered in Stage 2.

- S-STS (since last visit version)
- Vital signs (after at least 5 minutes of rest, sitting or supine)
- Body weight
- PE
- ECG (after at least 5 minutes supine rest)
- Laboratory tests

- Clinical chemistry (fasted)
- Hematology
- Plasma concentration blood sample
- RNA (miRNA, mRNA) PAXgene® blood sample (optional)
- Pregnancy test (urine) for women of childbearing potential
- Drug (urine) and alcohol screen (breathalyzer)
- Urinalysis
- Clinical measures
  - CAPS-5
  - PCL-5
  - HADS
  - CGI-S
  - PSQI
  - PSQI-A
  - BAC-Symbol Coding
  - ██████
  - DES-II
- Randomization (for Stage 2)
- Study drug accountability, compliance review, and dispensing (for next day dosing)
  - Medication adherence and reminder system review
- Concomitant medications
- AEs (serious and non-serious)

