### **2.1.2. Secondary Objectives**

The secondary objectives are

- To assess the effect of NYX-783 compared to placebo in the following outcomes: a) change in symptoms of PTSD as measured by the PTSD-Checklist for DSM-5 (PCL-5), b) change in sleep quality as measured by the Pittsburgh Sleep Quality Index (PSQI) Global Score, and c) change in cognitive function as measured by the Symbol Coding from the Brief Assessment of Cognition (BAC Symbol Coding).
- To assess the effect of NYX-783 compared to placebo in the change in global clinical severity of PTSD symptoms as measured by the Clinical Global Impressions-Severity (CGI-S) scale.
- To compare NYX-783 vs. placebo in the change in levels of anxiety and depression as measured by the Hospital Anxiety and Depression Scale (HADS).
- To assess the safety and tolerability of NYX-783 compared to placebo.

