## 4. Statistical Analysis and Reporting

### 4.1. Introduction

Data processing, tabulation of descriptive statistics, calculation of inferential statistics, and graphical representations will be performed primarily using SAS (release 9.4 or higher).

Continuous (quantitative) variable summaries will include the number of subjects (n) with non-missing values, mean, standard deviation (SD) (or standard error (SE) if appropriate), median, minimum, and maximum. Confidence intervals (CIs) will be added if appropriate.

Categorical (qualitative) variable summaries will be based on frequencies and percentages.

Unless stated otherwise, efficacy data for endpoints included in mixed effects repeated measures model (MMRM) analyses (groups [1], [2], [3], [7], [8], and [9]) will be summarized by visit and treatment group (Placebo, NYX-783 10 mg QD, NYX-783 50 mg QD) to allow for summary data treatment comparisons as per model inference.

Efficacy data for Stage 2 groups [4], [5], [6], [10], and [11] will be presented separately.

Unless stated otherwise, safety data will be summarized by Stage and treatment group (Placebo [as Placebo Only and Placebo Stage 2, separately], NYX-783 10 mg QD, NYX-783 50 mg QD); data presented by visit will be displayed based on the treatment group which applies at onset for AEs/collection date.

The minimum and maximum will be reported with the same degree of precision (i.e., the same number of decimal places) as the observed data. Measures of location (mean and median) will be reported to 1 degree of precision more than the observed data and measures of spread (SD, SE) will be reported to 2 degrees of precision more than the observed data.

Percentages will be presented to 1 decimal place, unless otherwise specified.

Unless otherwise indicated, all statistical tests will be conducted at a 0.10 significance level using one-sided tests and p-values will be reported. Corresponding 80% CIs (the interpretation of which is equivalent to a one-sided 90% CI when restricted to a single bound) will be presented.

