## 9.4. Clinical Laboratory Evaluations

Laboratory test results from hematology, serum chemistry, and urinalysis will be summarized descriptively (counts and percentages for categorical parameters) by treatment group, Stage and time point as both observed values and change from baseline values. Proportion of subjects with values < LLN and >ULN by treatment group, Stage and time point will be presented in summary tables.

The number of subjects with clinical laboratory values below, within, or above the normal range in relation to baseline will be tabulated for each clinical laboratory analyte by Stage and treatment group (bi-directional shift table) and visit. For those shift table, the most extreme post-baseline value will be used.

Urine drug screen, alcohol test and urine pregnancy test results will be presented in listings.

Potentially Clinically Significant (PCS) Laboratory Tests are defined as below

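### Stage 2 safety change uses different baselines for the drug arms and their randomized placebo controls; separately, the Stage 1 exposure time has no end date

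*SAP*

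**What the plan says.** **Baseline.** SAP 6.1.1 sets the Stage 2 safety baseline for re-randomized subjects: "the last non-missing observation before Week 4 will be used as baseline for Stage 2 data, with exception of groups [4] and [7". For the two excepted groups, "Changes from baseline for these groups will be based on the Stage 1 baseline given their study intervention remained unchanged". Protocol 14.4.1 identifies [4] and [7] as placebo and [5], [6], [8] and [9] as NYX-783. SAP 3.5 re-randomizes placebo responders and placebo non-responders 3:2:2, so [4] and [7] are the concurrent randomized controls. For efficacy, the next paragraph of 6.1.1 uses one rule: the baseline in every group from [4] to [11] "will be based on the last assessment prior to first dose of study drug in Stage 2".

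**Display.** Under SAP 4.1, "safety data will be summarized by Stage and treatment group (Placebo [as Placebo Only and Placebo Stage 2, separately", alongside the two doses. A secondary objective in SAP 2.1.2 is "To assess the safety and tolerability of NYX-783 compared to placebo".

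**Duration.** SAP 6.1.4 computes stage-specific duration as the date of the last dose, minus the date of the first dose in the Stage, plus one day. Only the first date is tied to the Stage. SAP 9.1 uses this duration as the denominator of event rates per patient-year, describes it as time on the assigned drug inside each Stage, and refers back to 6.1.4 for detail.

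**The concern.** Re-randomization at Week 4 makes the Stage 2 arms comparable, but change from baseline keeps that comparability only if every arm measures change from the same point. Here the drug arms start their clock later than their controls. Suppose the drug does nothing and a measure drifts by a mean of d between the two baseline points. The Stage 2 difference, drug minus placebo, is then −d.

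The outputs affected are Stage 2 change summaries, the shift tables in SAP 9.4 ("The number of subjects with clinical laboratory values below, within, or above the normal range in relation to baseline"), the creatinine limb that refers to baseline in SAP Table 2, and the vital-sign and weight flags in SAP Table 3. QTcF change in SAP 9.6 is affected if the Week 4 visit counts as baseline.

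The duration formula is a separate defect. SAP 6.1.4 assigns events to a Stage by onset, but the Stage 1 denominator runs on through Stage 2. For subjects on drug in Stage 1, the extra time is time on placebo.

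**Working it through.** The documents give no exposure, rate or safety-change figure to reproduce, so the check is day-count arithmetic on the rules as written.

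**Part (a): baseline**

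Inputs:
- Day 1, Week 2 (Day 14 ± 7), Week 4 (Day 28 ± 3), Week 6 (Day 42 ± 7) and Week 8 (Day 56 ± 3), from Protocol section 9 and Table 4.
- N = 156 at 4:1:1, with dropout of 15% in Stage 1 and 11% in Stage 2.

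The cut-off at Week 4 can be read two ways. Week 4 assessments precede Stage 2 dosing, because drug is dispensed there for use the next day: "Study drug accountability, compliance review, and dispensing (for next day dosing". The wording does not say whether that visit counts.

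- *Week 4 visit excluded.* Chemistry, vital signs, weight and S-STS fall back to Week 2 (Protocol 9.4, for example "Laboratory tests: clinical chemistry (fasted"). ECG, hematology and urinalysis are not taken at Week 2, so they fall back to Day 1 and match [4]/[7]. The drug arms' change in those three then includes four weeks before the drug.
- *Week 4 visit counts.* Baselines differ for every measure.

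| Change to | Drug, Week 2 baseline | Drug, Week 4 baseline | Placebo [4]/[7], Day 1 |
|---|---|---|---|
| Week 8 | 56 − 14 = 42 days (53 − 21 = 32 to 59 − 7 = 52) | 56 − 28 = 28 days (53 − 31 = 22 to 59 − 25 = 34) | 56 − 1 = 55 days (52 to 58) |
| Week 6 (nominal) | 42 − 14 = 28 days | 42 − 28 = 14 days | 42 − 1 = 41 days |

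Subjects concerned: Stage 1 placebo 156 × 4/6 = 104; re-randomized 104 × 0.85 = 88.4; Week 8 completers 88.4 × 0.89 = 78.7. Split 3:2:2, this is about 33.7 placebo and 22.5 per dose.

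An illustration on assumptions outside the documents uses the 7% weight flag, a Week 4 baseline for drug, a 4-week SD of weight change of 2% to 3%, independent increments and no drift. The flag rate is 2Φ(−7/SD), or 0.05% to 2.0%, on drug. It is 2Φ(−7/(SD√2)), or 1.3% to 9.9%, on placebo. The rule alone would then flag placebo more often.

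**Part (b): duration**

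Nominal dosing is Day 1 to 28 in Stage 1 and Day 29 to 56 in Stage 2 (SAP 7.4: Stage 2 dosing starts the day after the Week 4 visit).

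- Stage 1, as written: 56 − 1 + 1 = 56 days. Within stage: 28 − 1 + 1 = 28 days.
- Stage 2, either way: 56 − 29 + 1 = 28 days. Only Stage 1 is affected.

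At planned dropout, assuming exit mid-stage:
- Mean Stage 1 days within stage: 0.85 × 28 + 0.15 × 14 = 25.9.
- As written: 0.85 × (0.89 × 56 + 0.11 × 42) + 0.15 × 14 = 48.39.
- Ratio 48.39/25.9 = 1.87. Rates are understated by 1 − 25.9/48.39 = 46.5% (47.0% for exit at 5% of the stage, 46.0% at 95%).
- Drug arm of 26: 26 × 25.9/365.25 = 1.84 patient-years against 26 × 48.39/365.25 = 3.44. The 1.60 difference is Stage 2 placebo time.
- Ten events (assumed): 5.4 per patient-year within stage against 2.9 as written.

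Drug-to-placebo rate ratio within Stage 1, true value 1.00, placebo dropout 15%: it reads 0.97, 1.00 or 1.03 for drug-arm Stage 1 dropout of 5%, 15% or 25%.

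**The case against.** **On the baseline.** The exception is deliberate and explained: placebo did not change, so a pre-treatment baseline describes one continuous eight-week exposure, shown in its own column. SAP 9.4 and 9.5 also tabulate observed values, which give a fair randomized comparison in Stage 2 whatever the baseline. Stage 1 uses one baseline rule for all arms and also addresses the safety objective. Limits based only on ULN or on absolute values are untouched. The likely intent is that the Week 4 visit counts. The 32-to-52-day range uses the protocol's ± 7-day Week 2 window; the SAP's own schedule still shows ± 3 days, which would give 36 to 48.

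All of this is correct and narrows the reach of the problem. It does not remove it. The explanation justifies a description of continuous placebo, not a Stage 2 contrast with drug, and the Placebo Only column is the one set beside the drug columns. If the Week 4 visit does count, the mismatch is larger and covers every measure. The ± 7-day window is the one in the current protocol.

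**On duration.** The sentence in 6.1.4 is introduced as stage-specific, and SAP 9.1 makes the intent fairly plain, so a careful programmer might limit the last dose to the Stage. That stands as evidence of intent. But 9.1 defers to 6.1.4, the formula there qualifies only the first dose, and no visible section supplies a Stage 1 end date. The 46% figure is conditional on literal programming.

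**Conclusion.** Both parts hold and should be fixed.

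(a) Stage 2 change-from-baseline safety outputs compare drug and placebo over unequal periods on either reading. At Week 8 this is 28 against 55 days for all measures, or 42 against 55 days for the measures taken at Week 2. The size of any bias cannot be stated, because the documents give no time trend; the weight-flag percentages rest on assumed SDs.

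(b) If SAP 6.1.4 is programmed as written, Stage 1 rates per patient-year are understated by 46% to 47% at planned dropout. Drug-to-placebo rate ratios within Stage 1 barely move (0.97 to 1.03 over the dropout range examined). No claim is made about Stage 1 against Stage 2 rates, because the 7-day post-dose window for treatment-emergent events also affects them.

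Everything affected is descriptive safety output. Efficacy, subject counts and percentages, observed values, and limits based only on ULN or absolute values are unaffected.

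**What to change.** - **SAP 6.1.1:** use one Stage 2 safety baseline for all groups [4] to [11], namely the last non-missing value before the first Stage 2 dose, as already written for efficacy. This also settles that the Week 4 visit counts and names [10] and [11] explicitly. They appear to fall under the general rule already, since Protocol 7.1 and 7.2 call their move re-randomization, so naming them is only a clarification. Keep change from Day 1 for [4]/[7] as a supplementary display.
- **SAP 6.1.4:** define duration as last dose in the Stage minus first dose in the Stage, plus 1, and show the conversion to years (the variable is headed in years but the formula gives days). A completer then has 28 days in each stage, in agreement with SAP 9.1.

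The cost is SAP wording and programming. No change to data collection or sample size is needed.

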#### 6.1.2. Adjustments for Covariates

The primary efficacy endpoint will be evaluated using the weighted combination of the estimated treatment effects from the Stage-specific mixed models for repeated measures (MMRM). The MMRM models will include variables for treatment group, visit, treatment-by-visit interaction term, baseline CAPS-5 score and baseline-by-visit interaction.

#### 6.1.3. Handling of Dropouts or Missing Data

Missing efficacy data will be handled using MMRM's maximum likelihood method. No additional imputation is planned to be performed.

In general, there will be no substitutions made to accommodate missing data points. All data recorded on the case report form (CRF) will be included in data listings that will accompany the clinical study report.

##### 6.1.3.1. Handling of Missing Date Values

###### Partial or Missing Dates

The following conventions will be used to impute missing portions of dates for AEs. An AE with missing or incomplete start dates will be reported as treatment emergent for both Stages unless data provided clearly indicates an onset as occurring within a particular Stage (e.g. a month specific to Stage 1) or outside of the treatment-emergent period (e.g. year provided is prior to first dose of study drug) as defined in Section [6.1.4](#).

Partially available concomitant medication dates will be handled similarly with respect to identifying use as concomitant as defined in Section [9.7](#).

### 6.1.3.2. Imputation Methods and Sensitivity Analysis

Observed cases, without imputation, will be used for the majority of analyses.

If the relationship of an AE is missing, it will be considered possibly-related unless the event is not considered treatment-emergent as defined in Section 9.1. Missing AE severity will be coded as severe.

### 6.1.4. Derived Variables

- Actual treatment received: After unblinding, all blister cards dispensed will be unblinded. Actual treatment will be defined by stage as the higher dose received at least one time (one capsule) during the corresponding stage (50mg > 10mg > Placebo).
- CAPS-5 (Clinician Administered PTSD Scale for DSM-5) = The CAPS-5 is a 30-item structured interview for diagnosis and assessment of PTSD. CAPS-5 scores are derived at data-management level. CAPS-5 total symptom severity score is calculated by summing severity scores for the 20 DSM-5 PTSD symptoms. Similarly, CAPS-5 symptom cluster severity scores (subscores) are calculated by summing the individual item severity scores for symptoms corresponding to a given DSM-5 cluster: Criterion B, intrusions (items 1-5); Criterion C, avoidance (items 6-7); Criterion D, negative alterations in cognitions and mood (items 8-14); and, Criterion E, alterations in arousal and reactivity (items 15-20). The assessor combines information on frequency and intensity of an item into a single severity rating (0-4) for each of the 20 DSM-5 PTSD symptoms, with a maximum possible score of 80 points. A higher score corresponds to more severe PTSD.
- PCL-5 (PTSD Checklist for DSM-5) = The PCL-5 is a 20-item self-report measure that assesses PTSD symptoms experienced over the last week or month according to DSM-5 criteria. PCL-5 score is derived at data-management level. Items assess symptoms across 4 symptom clusters of PTSD (re-experiencing, negative mood, avoidance, and hyperarousal) on a 0-4 point Likert scale. Total scores range from 0-80. The “since last week” version should be used after screening. A higher score corresponds to more severe PTSD. PCL-5 response is defined as decrease (from baseline) of 10 points at the end of each stage (week 4/week 8) [6]. If total score is missing at one time point (Week4/Week8) then response will be set to missing. If patient early terminated and assessment at Week 4 or Week 8 missing then patient will be a non-responder. Baseline defined as in section 6.1.1.
- PSQI= The Pittsburgh Sleep Quality Index (PSQI) is a questionnaire to assess sleep quality and disturbances over a 1-month time interval. The score and subscores on this scale are derived by biostatistics. A total of 19 items are self-rated, 15 objective (about frequency of sleep disturbances and subjective sleep quality) and 4 subjective (typical bedtime, wake-up time, sleep latency and sleep duration) items. These 19 items generate 7 component scores: subjective sleep quality, sleep

latency, sleep duration, habitual sleep efficiency, sleep disturbances, use of sleeping medication, and daytime dysfunction, each of which ranges from 0: no difficulty to 3: severe difficulty. A global score  $>5$  indicates significant sleep disturbance. The algorithm to calculate PSQI score is detailed in [Appendix 1: PSQI Derivation](#). If response to any of these 19 items (except question 5J, if response to 5J is missing then it can be imputed to 0)) is missing, then PSQI score for that subject will be null.

- PSQIA= This is the addendum to the PSQI assessment assessing disruptive nocturnal behavior (DNB) in PTSD subjects based on 7 types of behaviors: 1) hot flashes, 2) general nervousness, 3) memories or nightmares of traumatic experience, 4) severe anxiety or panic, not related to traumatic memories, 5) bad dreams, not related to traumatic memories, 6) episodes of terror or screaming during sleep without fully awakening and 7) episodes of acting out dreams, such as kicking, punching, running, or screaming. Each DNB is rated on a scale of 0-3 (0: not in the past month, 1: less than once a week, 2: once or twice a week, and 3: three or more times a week), with a global score range of 0-21. Lower scores represent less disruptive behavior. PSQIA and is calculated by biostatistics in the following way:
  - Calculate number of non-missing monthly behavior scores responses. Call this count PSQIACNT. If PSQIACNT  $\geq 6$  then PSQIA score =  $(PSQIASUM/PSQIACNT)*7$  else set value to null. The score can range from 0 to 21.
- BAC Symbol Coding (Symbol Coding from the Brief Assessment of Cognition) = The Brief Assessment of Cognition (BACS) is a pen-and-paper cognitive assessment. BAC Symbol Coding is delivered on a Pathway tablet and offers a sensitive measure of processing speed. Participants are provided a key and asked to fill in the corresponding numbers beneath a series of symbols as quickly as possible within 90 seconds. The assessment takes approximately 3-5 minutes to complete, including instructions and practice. The measure represents the correct number of numerals (0-110); a higher count reflects a higher function.
- CGI-S (Clinical Global Impressions-Severity) = The CGI-S scale assesses the global severity of illness and change in clinical condition over time, and subjects are rated from 1 (normal, not at all ill) to 7 (among the most extremely ill subjects).
- HADS (Hospital and Anxiety Depression Scale) =The HADS is a self-assessment tool consisting of two subscales, one for anxiety (HADS-A) and one for depression (HADS-D). Each subscale consists of 7 items that are scored from 0-3, for a maximum score of 21 for either anxiety or depression; higher scores represent more severe anxiety or depression. HADS score are derived by biostatistics. HADS-A and HADS-D total scores will be computed only if the 7 items in each subscale are complete.

- DES-II (Dissociative Experiences Scale-II) =The Dissociative Experiences Scale-II (DES-II) is a 28 item, self-report questionnaire that measures a wide variety of dissociative experiences, from normal (e.g., day-dreaming) to pathological (depersonalization). The DES-II score is derived by data-management. Subjects rate the percentage of time they have the experience, from 0% to 100% (in increments of 10), the score is the sum of the individual items divided by 28. DES-II total score will be computed only if all the 28 individual questions are non-missing.
- Sheehan Suicidality Tracking Scale (S-STS) = The standard version of the S-STS is a 16-item scale that assesses the seriousness of suicidality phenomena on a Likert-type scale (0 to 4) ranging from 0 = “not at all” to 4 = “extremely.” The S-STS score will be derived by data-management. The S-STS accommodates a wide range of timeframes. In clinical trials, the frequently used variants are “in the past week”, “in the past month”, “since the last visit”, “lifetime look back”, and “in the past day.” In this study, during screening, "in the past month" version is used. For all the other visits "since the last visit" version of the S-STS is used.
- Subjects with high S-STS scores- Subjects with a score of 3 or 4 on any questions 2, 3, 4, 5, 6, 7, 8 or 13 in the S-STS questionnaire will be flagged.

- Placebo Non-responder = A Placebo Non-responder must satisfy the following criteria.
  - Randomized to placebo in Stage 1 of the study
  - Week 4 whose CAPS-5 total score reduction from baseline [Day 1]  $\leq 35\%$  and Week 4 CAPS-5 total score is  $\geq 26$
- Change from baseline = value at current visit – value at baseline (as defined in Section 6.1.1).
- TEAE = this is any adverse event with an onset date on or after first dose of study drug through 7 days after last dose of study drug. The Stage in which an event is considered treatment emergent will also be determined based on the relative onset timing against the first dose of Stage-specific study drug. Adverse Events with an onset during the 7 days after end of Stage 2 will be part of Stage 2.
- Duration of reported treatment period (years): For displays of TEAEs, it may be necessary to standardize rates of events due to variable treatment reporting periods. For Stage-specific reporting, durations are computed based on (the date of the last dose of study drug - the date of the first dose of Stage-specific study drug + 1).
- Treatment Related AEs= For each reported AE/SAE, the investigator assesses the relationship to study drug and categorize them into the following categories: Not Related = Unrelated and Unlikely Related, Related = Possibly Related and Probably Related). If an assessment is missing, then it will be treated as Related.
- Sexual Abuse= this is used to flag subjects who were victims of sexual abuse. If the medical history term preferred term is ‘Sexual Abuse’ or ‘Victim of Sexual Abuse’ then those subjects will be flagged as victim of sexual abuse.
- Time since start of Trauma (months) = date of randomization - date of index traumatic event (from medical history mhterm equals PTSD or POST TRAUMATIC STRESS DISORDER)
- High Avoidance Scores= Subjects with scores  $\geq 3$  in Q6 or Q7 or Q13, avoidance related questions in CAPS-5 questionnaire will be flagged. Data Adjustments/Handling/Conventions

All collected data will be presented in listings. Data not subject to analysis according to this plan will not appear in any tables or graphs but will be included only in the data listings.

All *P* values will be displayed in four decimals and rounded using standard scientific notation (e.g., 0.XXXX). If a *p* value less than 0.0001 occurs it will be shown in tables as <0.0001.

Adverse events will be coded using the MedDRA version 21.1 thesaurus.

